# **Imputation of Missing Medication Start Date**

Valid Portion	Missing Portion	Imputed Value for missing Portion
Month, Year	Day	Set Day = first day of that month and year
Year	Day, Month	Set date = January 1st of that year
None	Day, Month, Year	SV2 date

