## F.3 Medication Washout Period

Subjects not on antihypertensive medication(s) for a minimum of 4 weeks prior to SV1 are considered drug naïve and can proceed directly to SV2, within 3-4 weeks.

Following completion of Screening Visit 1, subjects on antihypertensive medication must be titrated off all antihypertensive medications over a 3-week washout period in a manner specified by the investigator. The washout period may be extended 1 additional week per investigator's discretion if it is judged necessary to allow the subject's blood pressure to stabilize off medications. Subjects with an office systolic blood pressure of  $<180$  mmHg after the minimum 3-week washout period will continue to Screening Visit 2 (SV2). Subjects with an office systolic blood pressure of  $\geq 180$  mmHg at any point during and after the washout period until procedure will be considered Screen Failures and will be exited from the study, as described in the *Subject Exit from Study* section of this Clinical Investigation Plan.

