## F.4 Two Week Screening Visit

The purpose of this visit is to assess the subject's office blood pressure two weeks after the antihypertensive medication washout period has been started. Drug-naïve patients do not need this visit. The target date is 2 weeks from the Screening 1 visit  $\pm 3$  days.

- a. **Office Blood Pressure** measurements will be obtained in accordance with Appendix L.7. This blood pressure measurement will not be used as the baseline BP measurement but will be used, in conjunction with the subject's medical history, to determine if, in the investigator's judgment, the subject's BP at Screening Visit 2 will qualify for inclusion in the study following the antihypertensive drug washout period. If the systolic OBP  $\geq 180$  mmHg, the subject must be exited from the trial. A subject who is drug naïve but still has a two week screening visit conducted, should be considered a screen failure if their office diastolic blood pressure is  $< 90$  mmHg when the subject is drug naïve at SV1 through the 2 week screening visit.
- b. **Clinical Assessment** will be conducted to further evaluate for prior or existing medical conditions that would exclude subjects from participation in the study and to establish the subject's baseline medical condition. An individual experienced in performing histories and physical exams is required to assess subjects for safety assessment during the period of time that study subjects are not on antihypertensive medications.
- c. **Medication & Adverse Event Reviews** will be completed to document baseline medication use and adverse events that occur after enrollment.

## F.5 Screening Visit 2

Screening Visit 2 must occur within 3-4 weeks of completion of SV1. The following assessments will be performed at Screening Visit 2:

- a. **EQ-5D:** The EuroQol (EQ-5D) instrument will be administered to measure baseline health outcomes.
- b. **SF-36:** The 36-Item Short Form Survey (SF-36) instrument will be administered to measure baseline health outcomes.
- c. **Clinical Assessment** will be conducted to further evaluate for prior or existing medical conditions that would exclude subjects from participation in the study and to establish the subject's baseline medical condition. An individual experienced in performing histories and physical exams is required to assess subjects for safety assessment during the period of time that study subjects are not on antihypertensive medications.

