## 5.3. Additional analyses

The following additional analyses will be conducted:

- Antihypertensive medication usage throughout the study, including escape subjects prior to 3-months and subjects reintroduced to medications after 3 months.
- Additional procedural characteristics e.g. treatment duration, frequency of distal renal artery treatment, ablations per vessel, location of ablations, number of ablations per patient and other characteristics will be analyzed to assess their impact on blood pressure.

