#### 9.7. Treatment Characteristics

Renal denervation treatment measures such as number of ablation attempts and number of generator codes will be summarized separately for each kidney, and for combined kidneys. Anti-hypertensive medication use will also be summarized at baseline and at each follow-up.

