# 12. Statistical Appendices

# 12.1. Appendix I: Imputation of Missing Dates

# **Imputation of Missing AE Onset Date**

Valid Portion	Missing Portion	Imputed Value for Missing Portion
Month, Year	Day	Set Day = first day of that month and year, then set the day = later of (New onset date, informed consent date).
Year	Day, Month	Set date = later of (January 1st of that year, informed consent date).
None	Day, Month, Year	Informed consent date.

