# **Imputation of Missing Medication Stop Date**

Valid Portion	Missing Portion	Imputed Value for missing Portion
Month, Year	Day	Set Day = first day of that month and year, then set the day = later of (New date, SV2 date, start date).
Year	Day, Month	Set date = later of (January 1st of that year, SV2 date, start date).

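### SAP 12.1 imputes missing medication start dates without bounds, so washed-out drugs can start after they stop and drugs restarted at 3 months appear as off-drug use in the descriptive tables

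*SAP*

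**What the plan says.** The medication start-date table in SAP 12.1 has three rows. With the day missing: "Set Day = first day of that month and year". With day and month missing: "Set date = January 1st of that year". With nothing known, the start becomes the SV2 date. None of the rows refers to any other date in the record.

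The two neighbouring tables do. A year-only adverse event onset is held at or after consent: "Set date = later of (January 1st of that year, informed consent date". A year-only stop date is held at or after SV2 and the start: "Set date = later of (January 1st of that year, SV2 date, start date". The stop-date rule acts on partial stop dates only; a complete stop date stays as recorded.

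The protocol sets the calendar on which these rules act:

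- Medication use is documented at SV1 (F.2), and then "subjects on antihypertensive medication must be titrated off all antihypertensive medications over a 3-week washout period" (F.3).
- "Screening Visit 2 must occur within 3-4 weeks of completion of SV1" (F.5).
- The procedure follows SV2 by at most 14 days, and the 3-month visit falls on day 76 to 104 after it.
- Drugs are re-introduced only after a valid 3-month ABPM (F.7, F.9).

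The SAP reports antihypertensive use throughout the study, "including escape subjects prior to 3-months and subjects reintroduced to medications after 3 months" (5.3). It adds that "Anti-hypertensive medication use will also be summarized at baseline and at each follow-up" (9.7), and 9.9.9 carries medication use through 36 months.

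**The concern.** The trial's premise is a drug-free interval between SV2 and the 3-month visit. An imputation rule for drug starts should therefore not move drugs across either edge of that interval. This one can do so at both ends.

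At the front edge, long-standing drugs are the ones most likely to have no known start. The rule gives them the SV2 date, which is after the washout in which they were withdrawn. At the back edge, a drug restarted at the 3-month visit is pulled back to the 1st of the month, to 1 January or to SV2, and so into or before the drug-free interval.

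What is at stake is the credibility of the medication tables. A drug in use before washout would drop out of any date-derived pre-washout summary. A subject who kept to the protocol could be tabulated as having taken drugs before 3 months, which is the category 5.3 sets apart as escape use.

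**Working it through.** The plan states no figure on this point, so there is none to reproduce. The check applies the SAP 12.1 rows to the protocol calendar.

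**(a) Washed-out drug, start wholly unknown, stop date complete.** Let SV2 fall W days after SV1 (W = 21 to 28) and let the drug stop s days after SV1.

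- Imputed start minus stop = W − s.
- Stopped at SV1 (s = 0): 21 to 28 days.
- Stopped the day before SV2 (s = W − 1): 1 day.

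Every stop before SV2 gives a start later than the stop. The imputed start is also later than SV1, so the drug is not active at SV1 by its dates. If the stop date is partial, the stop-date rule raises it to at least SV2 and no reversal occurs. The first-of-month and 1 January rows only move a start earlier, so they cannot produce the reversal.

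**(b) Drug begun on the day of the 3-month visit.** Assume that the visit is equally likely on each day of a 365-day year.

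*Day missing.* The imputed start precedes the visit unless the visit is on the 1st of a month: 365 − 12 = 353 dates, and 353/365 = 96.7%. The summed shift is 7 × (31 × 30/2) + 4 × (30 × 29/2) + (28 × 27/2) = 3255 + 1740 + 378 = 5373 days, and 5373/365 = 14.7 days on average. The largest shift is 30 days, less than the shortest SV2-to-visit interval of 76 days, so all 353 imputed starts fall between SV2 and the visit.

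*Day and month missing.* The imputed start precedes the visit on every date except 1 January: 364 of 365, by 182 days on average. With L days from SV2 to the visit, the start lies between SV2 and the visit on L dates and before SV2 on 364 − L dates:

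| L (days) | Between SV2 and visit | Before SV2 |
|---|---|---|
| 76 (day 76, procedure at SV2) | 76 (20.8%) | 288 (78.9%) |
| 97 (day 90, 7 days from SV2 to procedure) | 97 (26.6%) | 267 (73.2%) |
| 118 (day 104, 14 days from SV2 to procedure) | 118 (32.3%) | 246 (67.4%) |

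A start before SV2 makes the drug appear to run through the whole off-drug period.

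*Nothing known.* The start is SV2, so the drug again covers the whole period.

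*Sensitivity.* Because the ABPM lasts 24 hours, the true start may be the day after the visit. A true start on the 2nd of a month is then imputed to the visit date itself, so 12 more dates drop out: 353 − 12 = 341 (93.4%) with the day missing. The year-only count falls from 364 to 363.

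**The case against.** The strongest reply is that the harm is small and confined to tables. Much of that stands.

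- *Frequency.* The percentages describe the calendar once a date is incomplete; they do not estimate how many subjects are misclassified. Re-introduced drugs are started by the study investigator at a study visit. Protocol F.9 requires changes to be entered on the eCRF, so incomplete dates for restarts may be few. They are more plausible for long-standing drugs.
- *Primary endpoint and LOCF.* A reader might infer that a misdated drug could turn a valid 3-month value into a carried-forward one. The documents do not support this. SAP 9.1.3.1 defines escape by office SBP or safety reasons, and Protocol F.8 and F.17.2 have escape visits and escape medication changes recorded on the eCRF. Nothing says that escape is read from medication dates.
- *Per-protocol set.* A reader might also infer that compliant subjects would be excluded as violators. SAP 9.1.3.3 judges medication compliance by drug testing, not by dates.
- *Washed-out drugs at SV2 and later.* With a complete stop before SV2, the stop date already excludes the drug from those visits. A withdrawn drug is carried to SV2 only if its stop date is partial, which comes from the stop-date rule. The loss in case (a) is therefore limited to summaries of use before washout.
- *Medication index at 6 months (SAP 9.9.10).* A drug begun at 3 months and dated earlier is still counted at 6 months.
- *Year-only rule for old drugs.* For a drug taken before the trial, 1 January of the known year is a reasonable start. That row fails for drugs begun during the trial.

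The reply does not remove the defect. The rows are a stated rule that produces impossible or wrong dates in a washout design, and the SAP's other date tables carry the kind of bound that this one lacks.

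**Conclusion.** The concern holds for the descriptive medication summaries: use at baseline and at 3 months, and the split between escape before 3 months and re-introduction after it (SAP 5.3, 9.7, 9.9.9). When the start is wholly unknown and a complete stop precedes SV2, the drug interval is negative by 1 to 28 days. When a drug restarted at the 3-month visit has an incomplete start, it is dated before the visit on about 97% of calendar dates (day missing), on nearly all (year only), or always (nothing known).

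This rests on three assumptions: that the tables are derived from imputed dates, which the SAP does not state outright; that visit dates are spread evenly over the year; and that restarts occur at or just after the visit. The number of incomplete dates is not given, so the number of affected subjects cannot be estimated. No effect on the primary endpoint, on LOCF or on the per-protocol set is shown.

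**What to change.** Replace the start-date rows in SAP 12.1 with three rules:

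1. *Drug recorded at the SV1 medication review.* If the start is wholly unknown, set it to the consent/SV1 date and treat the drug as ongoing before then. If it is partial, keep the present rule, capped at the consent/SV1 date.
2. *Drug first recorded after SV1.* Use the date of the visit at which the eCRF shows it was prescribed. If none is recorded, use the later of the first day of the known month or year and the last visit whose medication review did not list the drug. If no part of the date is known, use that last visit alone. This fallback can still be early, by up to the gap back to that visit, so flag such records.
3. *Every imputed start.* Cap it at a known stop date.

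State also whether the escape versus re-introduction tabulation uses imputed dates. The stop-date table is a separate rule, and changing it would not repair this one.

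The cost is appendix wording and minor programming. The visit-level medication reviews are already collected.

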# **Imputation of Missing Medication Stop Date**

Valid Portion	Missing Portion	Imputed Value for missing Portion
Month, Year	Day	Set Day = first day of that month and year, then set the day = later of (New date, SV2 date, start date).
Year	Day, Month	Set date = later of (January 1st of that year, SV2 date, start date).
